10. PHARMACOKINETIC ANALYSES

The pharmacokinetic analyses will be based on the “Pharmacokinetic (PK)” population, unless otherwise specified.

Concentration-time data collected under protocol amendment 3 will be analysed using standard non-compartmental methods; some parameters will be determined for all participants and cycles. Full details are presented in [Appendix 12: List of Data Displays](#).

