9.4.10. Pharmacokinetic Analyses

Concentration-Time Data: Linear and semi-logarithmic individual concentration-time profiles, and mean and median profiles (when appropriate) will be plotted for belantamab mafodotin (ADC, total antibody and cys-mcMMAF). Concentrations will be listed for each participant and summarized (when appropriate) by planned time point and dose level.

Pharmacokinetic Parameters: PK analysis will be the responsibility of the CPMS department, GSK. Plasma belantamab mafodotin concentration-time data will be analysed by non-compartment methods using WinNonlin. Calculations will be based on the actual sampling times recorded during the study. For each dose and each participant, the following belantamab mafodotin (ADC, total antibody and cys-mcMMAF) PK parameters will be determined:

- 1) ADC and total antibody: after single dose: area under the plasma concentration-time curve (AUC(0-t), AUC(0- τ), and/or AUC(0- ∞), maximum observed plasma concentration (Cmax), time to Cmax (tmax), last time point where the concentration is above the limit of quantification (tlast), systemic clearance (CL), volume of distribution at steady state (Vss), terminal phase elimination rate (λz), terminal phase half-life (t½). After repeat dose: Ctrough.
- 2) cys-mcMMAF: after single dose, Cmax, Tmax, t½, AUC(0-168), and AUC(0-t) will be derived, and after repeat dose Ctrough.

PK parameters will be listed and summarized descriptively (mean, standard deviation, median, minimum, maximum, geometric mean, and the standard deviation, CV%, and 95% CI of log-transformed parameters) by cycle and dose level. PK data and other related information (i.e. participant demographics, baseline clinical status, etc.) from this study will be pooled with overseas data for further population PK analysis. Full details of analysis approaches will be provided in the RAP.

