2. SUMMARY OF KEY PROTOCOL INFORMATION

2.1. Changes to the Protocol Defined Statistical Analysis Plan

There were no changes or deviations to the originally planned statistical analysis specified in the protocol 208465/Amendment 3 (Dated: 26-Oct-2021).

[figure not shown]

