10.1.1. Non-compartmental Analysis

- Pharmacokinetic parameters described in [Table 2](#) below, will be determined separately for each analyte, as data permit.
- The pharmacokinetic parameters under protocol amendment 3 or later will be calculated by standard non-compartmental analysis according to current working practices and using Phoenix WinNonlin, version 6.3 or later, as data permit.
- The pharmacokinetic parameters CEOI and Ctrough will be determined directly from the concentration-time dataset for the other cycles under protocol amendment 3 and for participants enrolled prior to protocol amendment 3, as data permit.

Note: For the dosing occasions with only predose and end of infusion samples, the end of infusion concentration (CEOI) will not be identified as Cmax.

- All calculations of non-compartmental parameters will be based on actual sampling times.

Table 2 Derived Pharmacokinetic Parameters

Parameter	Parameter Description
AUC(0-t)	Area under the concentration-time curve from time zero to the time of the last quantifiable concentration (C(t)) will be calculated using the linear trapezoidal rule for each incremental trapezoid and the log trapezoidal rule for each decremental trapezoid
AUC(0- τ)	Area under the concentration-time curve during the dosing interval ($\tau=504h$, this parameter will be calculated only for ADC and total antibody)
AUC(0-168)	Area under the concentration-time curve from time 0 to 168h (This parameter will be calculated only for cys-mcMMAF)
AUC(0- ∞)	Area under the concentration-time curve extrapolated to infinity will be calculated as: $AUC = AUC(0-t) + C(t) / \lambda_z$
%AUCex	The percentage of AUC (0- ∞) obtained by extrapolation (%AUCex) will be calculated as: $[\text{AUC}(0-\infty) - \text{AUC}(0-t)] / \text{AUC}(0-\infty) \times 100$
Cmax	Maximum observed concentration, determined directly from the concentration-time data for each cycle. Cmax will not be derived when only predose and EOI samples were collected.
tmax	Time to reach Cmax, determined directly from the concentration-time data for each cycle

Parameter	Parameter Description
C_τ , C_{trough}	Trough concentration prior to the next dose for each cycle
CEOI	Observed plasma concentration at the end of infusion
$t_{1/2}$	Apparent terminal half-life will be calculated as: $t_{1/2} = \ln(2) / \lambda_z$
t_{last}	Time of last observed quantifiable concentration
CL	Clearance (This parameter will be calculated only for ADC and total antibody)

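### The SAP ties non-compartmental PK parameters to data under Amendment 3 or later, against the protocol's every-participant rule and the SAP's own statement of no changes

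*SAP*

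**What the plan says.** **Protocol.** Section 9.4.10 plans non-compartmental analysis (NCA) in WinNonlin with no reference to protocol version: "For each dose and each participant, the following belantamab mafodotin (ADC, total antibody and cys-mcMMAF) PK parameters will be determined". Section 9.4.1 says that deviations from the protocol's analysis plan will be documented in the RAP.

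**SAP text with a version condition.**
- Section 10: "Concentration-time data collected under protocol amendment 3 will be analysed using standard non-compartmental methods", followed by "some parameters will be determined for all participants and cycles".
- Section 10.1.1, second bullet: "The pharmacokinetic parameters under protocol amendment 3 or later will be calculated by standard non-compartmental analysis".
- Section 10.1.1, third bullet: CEOI and Ctrough are read directly from the data "for the other cycles under protocol amendment 3 and for participants enrolled prior to protocol amendment 3, as data permit".

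**SAP text without one.**
- Section 2.1: "There were no changes or deviations to the originally planned statistical analysis specified in the protocol 208465/Amendment 3".
- Section 10.1.1, first bullet: the Table 2 parameters "will be determined separately for each analyte, as data permit".
- Section 4: the PK population is every treated participant with at least one measurable PK sample.
- Section 14.6.5 plans NCA of the concentration-time data, by cycle and dose level.
- Tables 6.020 to 6.022 (derived PK parameters) are assigned to the PK population. Their only programming note is about transformed and untransformed values.

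**The concern.** A restriction by protocol version removes participants from an analysis that the protocol plans for all of them, and the SAP says that nothing has changed. The endpoint concerned is the first-listed secondary one, for which the protocol names AUC, Cmax and tmax as examples.

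The restriction matters because of where the sampling lies. Protocol 1.3, footnote 19, puts the full profile in Cycle 1. Later sampled cycles have too few points to rebuild these parameters, so a participant whose Cycle 1 preceded Amendment 3 cannot supply them from later visits.

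An analyst who follows 10.1.1 and one who follows 14.6.5 or the display list would run the same endpoint on different participants.

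**Working it through.** **1. Does the wording act as a cut-off?** Taken alone, the phrase in section 10 could simply name the current protocol. The third bullet of 10.1.1 rules that out for the NCA, because it treats participants enrolled before Amendment 3 as a separate group and assigns them two directly read quantities. Section 10 fits this: only some parameters are for all participants.

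**2. Who is in the earlier group?** Amendment 3 is dated 26-Oct-2021, and its rationale (SAP section 1) refers to two participants already on treatment. At least two were therefore enrolled before it. No document gives the total.

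**3. Could later cycles replace Cycle 1?** Sampling in footnote 19:
- Cycle 1: pre-dose, EOI, 2 h, 4 h, 8 h, 24 h, Day 4, Day 8, Day 15 = 9 samples (plus Day 22 only if the next dose is delayed).
- C2, C4, C6, C9, C12: pre-dose and EOI = 2 samples.
- Every sixth cycle after C12: 1 pre-dose sample.

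Two points do not give an AUC or a terminal slope, and Table 2 says "Cmax will not be derived when only predose and EOI samples were collected".

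**4. How many parameters are missing per earlier participant?** SAP Table 2 has 16 rows. The upper count assumes that only the quantities named in the third bullet survive. The lower count assumes that Cmax and tmax survive too, because Table 2 describes both as read straight from the concentration-time data in each cycle.

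| List | Applicable | Named for earlier participants | Missing | Missing if Cmax and tmax survive |
|---|---|---|---|---|
| Table 2, ADC and total antibody | 16 − 1 (AUC(0-168)) = 15 | CEOI, Ctrough | 15 − 2 = 13 | 13 − 2 = 11 |
| Table 2, cys-mcMMAF | 16 − 5 (AUC(0-τ), CL, CL/weight, Vss, Vss/weight) = 11 | CEOI, Ctrough | 11 − 2 = 9 | 9 − 2 = 7 |
| Protocol 9.4.10, ADC and total antibody | 11 | Ctrough | 11 − 1 = 10 | 10 − 2 = 8 |
| Protocol 9.4.10, cys-mcMMAF | 6 | Ctrough | 6 − 1 = 5 | 5 − 2 = 3 |

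The 11 in the third row are three AUCs (joined by and/or in the protocol), Cmax, tmax, tlast, CL, Vss, λz, t½ and Ctrough. The 6 in the fourth are Cmax, tmax, t½, two AUCs and Ctrough.

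**5. Effect on precision, as an illustration only.** Assume six participants at one dose level and an unchanged SD. The half-width of the 95% CI for a log-transformed parameter, in SD units, is t(0.975, n−1)/√n.
- n = 6: 2.5706/2.4495 = 1.049
- n = 5: 2.776/2.236 = 1.242; ratio 1.242/1.049 = 1.18
- n = 4: 3.182/2 = 1.591; ratio 1.591/1.049 = 1.52

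Dropping one of six widens the interval on the log scale about 1.18 times, and dropping two about 1.52 times.

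**The case against.** The strongest reply is that the SAP as a whole points to the wider analysis. Section 10 sends the reader to Appendix 12 for details, and the displays there use the PK population without a version limit. Section 14.6.5 plans the NCA without one. The endpoint is secondary, descriptive and qualified by what the data permit. This lowers the practical risk, but it does not remove the conflict. Section 10 applies the PK population only unless otherwise specified, and 10.1.1 can be read as specifying otherwise. The data qualifier concerns whether a profile is adequate, and a protocol date is not a data limitation. Nor does the Amendment 3 summary of changes list any new Cycle 1 PK sampling that would explain a cut-off.

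Four stronger readings are tempting and are not supported:
- **Cmax and tmax are certainly lost.** Table 2 says that they come directly from the data for each cycle and excludes only occasions with pre-dose and EOI samples alone. Cycle 1 has nine. The third bullet of 10.1.1 does not mention them, so their loss is possible but not established.
- **The accumulation ratios are restricted too.** Section 10.3.1.2 refers to data collected under Protocol 208465/Amendment 3, but SAP sections 1 and 2.1 use the same label for the governing protocol. There is no before-and-after contrast in 10.3.1.2. The wording is ambiguous, and protocol 9.4.10 lists no accumulation ratio in any case.
- **No participant qualifies, so the tables hold only CEOI and Ctrough.** The extension of the study for two ongoing participants makes closed enrolment plausible, but no document states it.
- **The loss can be sized on all participants pooled.** The protocol and SAP 14.6.5 summarise by dose level, so a pooled interval is not a planned output.

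**Conclusion.** The wording conflict stands, with high confidence. SAP 10 and the second and third bullets of 10.1.1 limit NCA by protocol version. Protocol 9.4.10 does not, SAP 2.1 declares no departure, and other parts of the SAP omit the limit.

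Under the literal reading, each participant whose Cycle 1 preceded Amendment 3 gives no AUC, CL, Vss, λz or half-life. The total missing is 11 to 13 of 15 Table 2 parameters (ADC and total antibody) or 7 to 9 of 11 (cys-mcMMAF). Against the protocol's list it is 8 to 10 of 11, or 3 to 5 of 6. The range reflects the unsettled status of Cmax and tmax.

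The number of participants affected is at least two and otherwise unknown. The widening of 1.18 or 1.52 times rests on the assumed six at one dose level and is not an estimate for this trial. No data are lost. Concentration summaries and plots, CEOI, Ctrough and the pooled population PK analysis are unaffected.

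**What to change.** **Main edit.**
- SAP 10: remove the condition that the data were collected under Amendment 3.
- SAP 10.1.1, second bullet: remove the condition on Amendment 3 or later.
- SAP 10.1.1, third bullet: remove both references to Amendment 3, so that it covers the other cycles as data permit.
- Add a sentence: NCA, including Cmax and tmax, uses the Cycle 1 profile of every PK-population participant with adequate data, whatever the protocol version; CEOI and Ctrough are read directly for later sampled cycles.

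**For clarity.** Remove the reference to data collected under Protocol 208465/Amendment 3 from 10.3.1.2.

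**Editorial.** The first paragraph of 10.3.1.2, and 14.5.3, speak of Ctrough at Cycle 4. The explicit formula in 10.3.1.2 uses the Cycle 3 trough (pre-dose C4D1) over the Cycle 1 trough. The formula settles the meaning; align the other two places with it.

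**If the limit is deliberate.** Declare and justify it in SAP 2.1, and carry it through the first bullet of 10.1.1, section 14.6.5 and the table notes.

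**Cost.** SAP wording only: no new samples and no protocol amendment.

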10.1. Drug Concentration Measures

Refer to [Appendix 5: Data Display Standards & Handling Conventions](#) (Section 14.5.3)

10.1.1. Non-compartmental Analysis

- Pharmacokinetic parameters described in [Table 2](#) below, will be determined separately for each analyte, as data permit.
- The pharmacokinetic parameters under protocol amendment 3 or later will be calculated by standard non-compartmental analysis according to current working practices and using Phoenix WinNonlin, version 6.3 or later, as data permit.
- The pharmacokinetic parameters CEOI and Ctrough will be determined directly from the concentration-time dataset for the other cycles under protocol amendment 3 and for participants enrolled prior to protocol amendment 3, as data permit.

Note: For the dosing occasions with only predose and end of infusion samples, the end of infusion concentration (CEOI) will not be identified as Cmax.

- All calculations of non-compartmental parameters will be based on actual sampling times.

Table 2 Derived Pharmacokinetic Parameters

Parameter	Parameter Description
AUC(0-t)	Area under the concentration-time curve from time zero to the time of the last quantifiable concentration (C(t)) will be calculated using the linear trapezoidal rule for each incremental trapezoid and the log trapezoidal rule for each decremental trapezoid
AUC(0- τ)	Area under the concentration-time curve during the dosing interval ($\tau=504h$, this parameter will be calculated only for ADC and total antibody)
AUC(0-168)	Area under the concentration-time curve from time 0 to 168h (This parameter will be calculated only for cys-mcMMAF)
AUC(0- ∞)	Area under the concentration-time curve extrapolated to infinity will be calculated as: $AUC = AUC(0-t) + C(t) / \lambda_z$
%AUCex	The percentage of AUC (0- ∞) obtained by extrapolation (%AUCex) will be calculated as: $[\text{AUC}(0-\infty) - \text{AUC}(0-t)] / \text{AUC}(0-\infty) \times 100$
Cmax	Maximum observed concentration, determined directly from the concentration-time data for each cycle. Cmax will not be derived when only predose and EOI samples were collected.
tmax	Time to reach Cmax, determined directly from the concentration-time data for each cycle

Parameter	Parameter Description
C_τ , C_{trough}	Trough concentration prior to the next dose for each cycle
CEOI	Observed plasma concentration at the end of infusion
$t_{1/2}$	Apparent terminal half-life will be calculated as: $t_{1/2} = \ln(2) / \lambda_z$
t_{last}	Time of last observed quantifiable concentration
CL	Clearance (This parameter will be calculated only for ADC and total antibody)
CL/weight	CL normalized by body weight (This parameter will be calculated only for ADC and total antibody)
V_{ss}	Volume of distribution at steady state (This parameter will be calculated only for ADC and total antibody)
$V_{ss}/weight$	V_{ss} normalized by body weight (This parameter will be calculated only for ADC and total antibody)
λ_z , λ_z	Terminal phase rate constant

10.2. Population of Interest

The pharmacokinetic analyses will be based on the PK population, unless otherwise specified.

10.3. Statistical Analyses / Methods

Details of the planned displays are provided in [Appendix 12: List of Data Displays](#), based on GSK data standards and statistical principles. Unless otherwise specified, endpoints / variables defined in [Section 10.1.1](#) will be summarised using descriptive statistics descriptively (mean, standard deviation, median, minimum, maximum, geometric mean, and the standard deviation, CV%, and 95% CI of parameters values) by cycle, graphically presented (where appropriate) and listed.

10.3.1. Statistical Methodology Specification

The following pharmacokinetic statistical analyses will only be performed if sufficient data are available.

10.3.1.1. Concentration-Time Data

Concentration-time data will be summarized (when appropriate) using mean, median, standard deviation, minimum, and maximum, i.e. by planned time point and dose level for belantamab mafodotin (ADC, total antibody and cys-mcMMAF).

Linear and semi-logarithmic individual concentration-time profiles, and mean and median profiles (when appropriate) will be plotted for belantamab mafodotin (ADC, total antibody and cys-mcMMAF).

10.3.1.2. Pharmacokinetic Parameters

To assess the extent of accumulation following belantamab mafodotin repeat dosing, the observed accumulation ratio (Ro) for belantamab mafodotin, total antibody, and cys-mcMMAF will be determined as ratio of CEOI and Ctrough at Cycle 4 to CEOI and Ctrough at Cycle 1, respectively, using the data collected under Protocol 208465/Amendment 3.

Previous studies indicate that the pharmacokinetics for the third consecutive dose given at the planned interval will be at steady state. Therefore, based on the planned sampling scheme, accumulation ratios will be derived using the CEOI at Cycle 4 for Ro(CEOI) and Ctrough at Cycle 3 (predose at C4D1) for Ro(Ctrough). Participants must receive the same dose without delay or change for the first three cycles to derive Ro(Ctrough) and for the first four cycles to derive Ro(CEOI) (i.e., with dosing delays of ≤ 3 days).

$Ro(CEOI) = CEOI \text{ at C4D1} / CEOI \text{ at C1D1};$

$Ro(Ctrough) = \text{Cycle 3 trough} / \text{Cycle 1 trough}$

Accumulation ratios of CEOI and Ctrough, and other Pharmacokinetic Parameters in [Table 2](#) will be summarised using descriptive statistics for belantamab mafodotin (ADC, total antibody and cys-mcMMAF) by planned initial dose level, graphically presented (where appropriate) and listed.

CCI

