- 17. Echocardiography for LVEF performed within 3 months of screening are acceptable as screening value. For participants with an abnormal LVEF (per institutional standards), the participant is to follow-up with a cardiologist.
- 18. ECGs on dosing days: Triplicate ECGs to be performed at pre-dose (within 30 minutes prior to SOI) and EOI at cycle 1. Triplicate ECGs should be collected prior to PK sample on Cycle 1 Day 2, Day 4, Day 8 and Cycle 1 Day 15. Single ECG at screening, at all other cycles, and End of Study Treatment. On days where ECG time points align with PK sampling time points, ECGs must be performed within 30 minutes prior to PK samples being drawn (PK sample must be taken at the exact nominal time). ECGs will be collected and stored at site. See SRM for details on collection regarding ECGs.
- 19. PK samples to be taken in all participants for belantamab mafodotin ADC, total antibody and cys-mcMMAF measurements on:
 - C1D1 at pre-dose (within 30 minutes prior to SOI), at the end of infusion (EOI) (+5 min), 2 h post-SOI (±15 min), 4 h post-SOI (±15 min), 8 h post-SOI (±1 h), 24 h post-SOI (±2 h);
 - C1D4 anytime (±1 day);
 - C1D8 anytime (±1 day);
 - C1D15 anytime (±1 day);
 - C1D22 anytime (±1 day) (collect one PK sample only if the dose for the next cycle is delayed; this sample will combined)
 - For C2D1, C4D1, C6D1, C9D1, and C12D1, collect samples at pre-dose (within 30 min prior to SOI) and at the EOI (+5 min);
 - For every six cycles after C12 (e.g., C18, C24, etc.), collect one sample at pre-dose (within 30 min prior to SOI). However, one year after the first dose of last subject, PK samples will only be collected for the interpretation of ADA results in the following visits.
- 20. Collect 1 PK sample at each participant's final visit.
- 21. All ADA samples will be collected prior to each infusion at C1, C2, C4, C6, C9, C12, and every 6 cycles thereafter (C18, C24, etc.) until end of treatment (dosing days only) and at the last visit.
- 22. Disease Response Assessment: Response assessment must be conducted Q3W based on standard disease laboratory tests (serum and urine M protein test, FLC, IgD/E, if applicable), Ca corrected for albumin, bone marrow aspirate (in case of CR, or suspected PD if not evident otherwise). Assessment based on imaging has to be included in

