2.3.3. Pharmacokinetics and Pharmacodynamics

The pharmacokinetics and pharmacodynamics of belantamab mafodotin (antibody-drug conjugate, including complex) with CCI), total monoclonal antibody (total mAb; including complex), and cys-mcMMAF were investigated in 291 participants with RRMM following IV administration at doses from 0.03 to 4.6 mg/kg Q3W in Study BMA117159 (n=73) and at doses of 2.5 or 3.4 mg/kg Q3W in Study 205678 (n=218).

Maximum concentrations (Cmax) of belantamab mafodotin and total monoclonal antibody were observed at or shortly after the end of infusion (EOI), while cys-mcMMAF Cmax values were generally observed on Day 2. On a molar basis, plasma concentrations of cys-mcMMAF were <1% of belantamab mafodotin concentrations. There was limited accumulation (less than 2-fold) of belantamab mafodotin or cys-mcMMAF during subsequent cycles.

Belantamab mafodotin pharmacokinetics were well described by a linear, two-compartment population model, with a time-varying decrease in clearance in a population

pharmacokinetic analysis. At Cycle 1, belantamab mafodotin had a systemic clearance of 0.92 L/day, steady-state volume of distribution of 11 L, and an elimination half-life of 12 days in participants with RRMM in Study 205678. Over time, clearance was reduced by 28%, resulting in an elimination half-life of 14 days. The time to 50% change in clearance was approximately 50 days.

No clinically significant differences in the pharmacokinetics of belantamab mafodotin or cys-mcMMAF were observed based on age (34 to 89 years), sex, race (African American/Black and White), body weight (42 to 130 kg), mild or moderate renal impairment (eGFR \geq 30 ml/min/1.73m²) or mild hepatic impairment (NCI-ODWG classification). Higher serum levels of β_2 -microglobulin, IgG, and column and lower levels of albumin are associated with more advanced multiple myeloma or a higher multiple myeloma disease burden. Higher baseline IgG and levels, and lower baseline albumin levels were associated with higher belantamab mafodotin clearance leading to lower average and trough concentrations (Ctau) of belantamab mafodotin. Higher baseline IgG and levels were associated with higher cys-mcMMAF central volume of distribution leading to lower cys-mcMMAF Cmax.

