In nonclinical studies, cys-mcMMAF had limited metabolic clearance. *In vitro* data suggested that belantamab mafodotin and cys-mcMMAF are unlikely to perpetrate a drug-drug interaction or to be a victim of a drug-drug interaction with inhibitors or inducers of cytochromes (CYP) P450. Cys-mcMMAF was an *in vitro* substrate of organic anion transporting polypeptides (OATP)1B1 and OATP1B3, multidrug resistance associated proteins (MRP)1, MRP2, and MRP3, a borderline substrate of bile salt export pump (BSEP), and a possible substrate of P-glycoprotein (P-gp). Following the administration of belantamab mafodotin to participants with RRMM, only intact cys-mcMMAF was detected in pooled human urine, with no evidence of other MMAF-related urinary metabolites.

Free CCI levels were measured in Study BMA117159 and Study 205678. All participants exhibited reductions in free CCI concentration at end of infusion compared to baseline at Cycle 1, with a return to near-baseline level by 7 days after dosing, reflecting binding of belantamab mafodotin to CCI Maximum decreases ranged from 2% to 97%, which were qualitatively dose-dependent, with larger reductions in free CCI at higher doses.

Exposure-response analyses performed for Study 205678 and/or Study BMA117159 found that ocular safety endpoints were most strongly associated with belantamab mafodotin exposure, while efficacy endpoints had a weaker association with belantamab mafodotin exposure. Both safety and efficacy endpoints were associated with patient characteristics. Belantamab mafodotin Ctau was associated with probability of corneal events and keratopathy and cys-mcMMAF Cmax was associated with probability of thrombocytopenia. Probability of occurrence of dry eye, blurred vision, neutropenia and infusion related reaction were not associated with an exposure measure. In addition, the results of the analysis of concentration against corrected QT interval (QTc) demonstrated that belantamab mafodotin or cys-mcMMAF did not have a significant effect on cardiac repolarization.

Details of the characteristics of belantamab mafodotin, nonclinical, and clinical activity are provided in the Investigator's Brochure (IB) [Belantamab mafodotin GlaxoSmithKline Document Number RPS-CLIN-004867, 2021].

This is the first study for belantamab mafodotin in China to assess the safety, tolerability, pharmacokinetics (PK), immunogenicity and clinical activity of belantamab mafodotin in Chinese participants with MM.

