Neutropenia	Grade ≥3 Defined as ANC <1.0x10 ⁹ /L	 If noted on Day 1 of any cycle, withhold belantamab mafodotin. Consider more frequent hematology (CBC) monitoring as clinically indicated, until recovery to Grade 2 or less. Resume belantamab mafodotin at pre-held dose once neutropenia recovers to Grade ≤ 2 (ANC ≥ 1.0x10⁹/L) on Day 1 of the subsequent cycle. Prophylactic antibiotics, per physician discretion and local institutional guidance. Consider growth factors. Local guidance must be followed for hematological monitoring, if more conservative than the protocol SoA specifications. In cases of frequent recurrent neutropenia (ANC <1.0x10⁹/L), consider dose reduction of belantamab mafodotin by 1 level
	2	Stop the infusion, provide medical treatment and continue at half the original infusion rate after resolution to Grade 0-1. Any future infusion needs to be pre-medicated.
Infusion Reaction ^b	3	 Further treatment with belantamab mafodotin needs to be discussed with Medical Monitor. Continuation only allowed after recovery to ≤Grade 1 and with pre-medication, and extension of infusion time to 2-4 hours. Any future infusion needs to be pre- medicated.
	4	Permanently discontinue from study treatment
Pneumonitis	2	 Withhold treatment with belantamab mafodotin Upon recovery, restart treatment with 1 dose level reduction. If patient is already at the lowest dose level (1.9 mg/kg), then rechallenge with the same dose must be discussed with the Medical Monitor
	Grade 3-4	Permanently discontinue from treatment

a. Medical Monitor may consult GSK's nephrotoxicity panel about plans to continue therapy.

b. If symptoms resolve within one hour of stopping infusion, the infusion may be restarted at 50% of the original infusion rate (e.g., from 100 mL/hr to 50 mL/hr). Otherwise dosing will be held until symptoms resolve and the participant must be pre-medicated for the next scheduled dose.

Table 6 General Dose Modification and Management Guidelines for Drugrelated Adverse Events Not Otherwise Specified

Severity	Management	Follow-up
Grade 1	 Administer symptomatic treatment as appropriate Continue study drug(s)^a 	Provide close follow-up to evaluate for increased severity, no dose modification necessary

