14.12.14. Pharmacokinetic Tables

Pharmacokinetic Tables					
No.	Population	GSK Standard / Example Shell	Title	Programming Notes	Deliverable [Priority]
PK Concentration Data					
6.010	PK	PK01	Summary of Plasma Belantamab Mafodotin (ADC) PK Concentration-Time Data		SAC [1]
6.011	PK	PK01	Summary of Plasma Belantamab Mafodotin (Total Antibody) PK Concentration-Time Data		SAC [1]
6.012	PK	PK01	Summary of Plasma cys-mcMMAF PK Concentration-Time Data		SAC [1]
PK Parameter Data					
6.020	PK	PK06	Summary of Derived Belantamab Mafodotin (ADC) PK Parameters	PK06 with both transformed and untransformed values.	SAC [1]
6.021	PK	PK06	Summary of Derived Belantamab Mafodotin (Total Antibody) PK Parameters	PK06 with both transformed and untransformed values.	SAC [1]
6.022	PK	PK06	Summary of Derived cys-mcMMAF PK Parameter	PK06 with both transformed and untransformed values.	SAC [1]
Accumulation Ratio					
6.023	PK	PK05	Summary of Results of Accumulation Ratio Assessment for Belantamab Mafodotin (ADC)	Include Ro(CEOI) and Ro(Ctrough) with 95%CI in one table.	SAC [1]
6.024	PK	PK05	Summary of Results of Accumulation Ratio Assessment for Belantamab Mafodotin (Total Antibody)	Include Ro(CEOI) and Ro(Ctrough) with 95%CI in one table.	SAC [1]
6.025	PK	PK05	Summary of Results of Accumulation Ratio Assessment for cys-mcMMAF	Include Ro(CEOI) and Ro(Ctrough) with 95%CI in one table.	SAC [1]

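### For cys-mcMMAF, the planned end-of-infusion accumulation ratio divides by a small Cycle 1 value that depends on infusion length, so it is a poor measure of accumulation

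*SAP*

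**What the plan says.** **SAP 10.3.1.2** sets out to assess accumulation on repeat dosing: "the observed accumulation ratio (Ro) for belantamab mafodotin, total antibody, and cys-mcMMAF will be determined as ratio of CEOI and Ctrough". Ro(CEOI) is CEOI at C4D1 over CEOI at C1D1. Ro(Ctrough) is the Cycle 3 trough (the C4D1 pre-dose sample) over the Cycle 1 trough. Both apply to all three analytes. A participant contributes only if the dose is unchanged and no delay exceeds 3 days. Infusion duration is not mentioned.

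**SAP 14.12.14** has a separate table, 6.025, "Summary of Results of Accumulation Ratio Assessment for cys-mcMMAF", which holds both ratios with 95% CIs. Listing 1.320 gives the individual values.

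**SAP 10.1.1** says that at visits with only pre-dose and end-of-infusion samples CEOI is not treated as Cmax, and its Table 2 does not derive Cmax there.

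**Protocol 2.3.3** says ADC and total antibody peak at or shortly after the end of infusion, "while cys-mcMMAF Cmax values were generally observed on Day 2". From the earlier studies it also reports: "There was limited accumulation (less than 2-fold) of belantamab mafodotin or cys-mcMMAF during subsequent cycles".

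**Protocol 1.3, footnote 19**, takes later samples on C1D1 at "8 h post-SOI (±1 h), 24 h post-SOI (±2 h". After Cycle 1 the rule is: "For C2D1, C4D1, C6D1, C9D1, and C12D1, collect samples at pre-dose (within 30 min prior to SOI) and at the EOI (+5 min".

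**Protocol 6.1.1** allows an infusion of about 30-60 min. Table 5 (section 6.6) has the infusion continue at half the original rate after a Grade 2 reaction. If treatment continues after a Grade 3 reaction, it requires "extension of infusion time to 2-4 hours".

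**The concern.** An accumulation ratio is informative when numerator and denominator sit at comparable points of the profile and the denominator is a substantial part of exposure. For ADC and total antibody, the end of infusion is close to the peak and meets that test. For cys-mcMMAF it falls early in a rise that lasts about a day. In Cycle 1 the rise starts from zero, so the denominator is small.

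Two things then drive the ratio. Residual drug that is minor against the peak can be large against that denominator. And because the early rise is nearly linear, the value at the end of infusion depends on how long the infusion ran.

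At stake is the reading of one secondary PK output. A cys-mcMMAF ratio of 3 or 0.7 in Table 6.025 could be taken as a change in exposure when peak and trough have barely moved. With up to six evaluable participants per cohort, one participant with unequal infusion times can shift the summary.

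**Working it through.** The plan states no accumulation figure to reproduce, so this is an illustration of the planned statistic.

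**Inputs from the documents:** dosing every 504 h; infusion 30-60 min; cys-mcMMAF peak generally on Day 2; ADC half-life 12 days at Cycle 1 (Protocol 2.3.3).

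**Assumptions:** cys-mcMMAF tmax exactly 24 h; linear kinetics; first-order appearance and loss driven by a constant-rate infusion; half-life 3, 7 or 10 days, because the documents give none.

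**Formulas.** Let e(T) be the Cycle 1 concentration at the end of an infusion of length T. Let c be what remains from the three earlier doses at the same moment in Cycle 4. By superposition:

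- equal infusions: Ro(CEOI) = (e + c)/e = 1 + c/e
- unequal infusions: Ro(CEOI) = (e(T4) + c)/e(T1)

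**Equal infusions** (e and c as % of Cycle 1 Cmax):

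| Half-life | e, 30 min | e, 60 min | c | Ro(CEOI), 30 min | Ro(CEOI), 60 min | True peak ratio | Ro(Ctrough) |
|---|---|---|---|---|---|---|---|
| 3 d | 3.45 | 6.77 | 1.08 | 1.31 | 1.16 | 1.01 | 1.01 |
| 7 d | 4.17 | 8.13 | 16.1 | 4.87 | 2.98 | 1.15 | 1.14 |
| 10 d | 4.52 | 8.78 | 32.7 | 8.24 | 4.72 | 1.31 | 1.29 |

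Example, 7 days and 60 min: 1 + 16.1/8.13 = 2.98. Carry-over of 16% of the peak looks like a threefold increase because it is divided by 8% of the peak.

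**Unequal infusions, 3-day half-life** (true peak ratio 1.01):

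- 60 min in Cycle 1, 30 min in Cycle 4: (3.45 + 1.08)/6.77 = 0.67
- 30 min in Cycle 1, 60 min in Cycle 4: (6.77 + 1.08)/3.45 = 2.3

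Both pairs of durations are inside the permitted range.

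**Contrast with ADC** (one compartment, 12-day half-life held constant). The ratio after four doses 21 days apart is 1 + 2^(-1.75) + 2^(-3.5) + 2^(-5.25) = 1 + 0.297 + 0.088 + 0.026 = 1.41. Moving from 30 to 60 min changes CEOI by about 0.1%. The weakness is therefore specific to cys-mcMMAF.

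**What the samples can support.** Cycle 1 has a 24 h sample; Cycle 4 stops at the end of infusion. The cys-mcMMAF peak is not observed in Cycle 4. The trough ratio needs only the C2D1 and C4D1 pre-dose samples, both of which are scheduled.

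**The case against.** **The SAP does not claim to measure peak accumulation.** This stands. The outputs are labelled as CEOI and Ctrough ratios, and section 10.1.1 declines to equate CEOI with Cmax. A reader might infer that Table 6.025 will present peak accumulation; the documents do not say so. Residual drug from earlier cycles is also genuine accumulation. What remains is that the caution about CEOI is not carried into the definition of Ro, the table or the listing, and that this ratio follows neither the peak nor the trough.

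**Values below quantification are covered.** Largely true. A reader might infer that an unquantifiable Cycle 1 CEOI leaves an undefined ratio with no rule. But parameters are derived as data permit, these analyses run only with sufficient data (SAP 10.3.1), and SAP 14.5.3 invokes a standard for parameters affected by such values.

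**The size rests on assumptions.** Also true. With a 3-day half-life and equal infusions the ratio is only 1.16-1.31. Day 2 is itself limited by the sampling grid of 8 h, 24 h and Day 4. The direction follows from a late peak; the size does not.

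**Infusion times may not differ.** The distortion needs different durations within a participant, and the 2-4 h extension applies only when treatment continues after a Grade 3 reaction. But 30-60 min already spans a factor of two. Protocol 2.3.2 also reports infusion reactions in 21% at 2.5 mg/kg in the phase II study, mostly at the first infusion, which is the denominator visit.

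**No decision hangs on it.** A reader might infer a planned comparison with the earlier statement of limited accumulation, or a link to thrombocytopenia because "cys-mcMMAF Cmax was associated with probability of thrombocytopenia". Neither is planned for Ro(CEOI). The optional exposure-response work names Cmax and AUC among its exposure measures, not this ratio.

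**Conclusion.** The concern holds in a limited form. Followed as written, the SAP will produce a cys-mcMMAF end-of-infusion ratio with a small denominator that depends on infusion length. It can depart widely from the change in peak or trough. Under the stated assumptions it runs from 1.16 to 4.72 (60 min) or 1.31 to 8.24 (30 min) while the true peak ratio runs from 1.01 to 1.31. Unequal but permitted infusion times can give 0.67 or 2.3 with almost no true change. These figures depend on the assumed half-life and tmax and do not predict the trial's results.

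The stronger reading, that the SAP will misreport peak accumulation and so mislead on safety, is not supported. Severity is low. The statistic is descriptive and secondary and does not touch the primary endpoint. Dose-escalation meetings follow the 21-day DLT window, before a cohort reaches C4D1.

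**What to change.** In SAP 10.3.1.2, Table 6.025 and Listing 1.320, limit Ro(CEOI) to ADC and total antibody. For cys-mcMMAF, report Ro(Ctrough) only, where both troughs are quantifiable. This fits Protocol 9.4.10, which lists only Ctrough as the repeat-dose parameter for cys-mcMMAF (and for the other two analytes).

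If Ro(CEOI) is kept for cys-mcMMAF:

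- restrict it to participants whose actual C1D1 and C4D1 infusion durations match, within a tolerance stated in advance;
- list both durations beside each ratio (start and end times are already recorded in the eCRF);
- footnote that it does not reflect accumulation of Cmax or of overall exposure.

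The cost is a wording change and one descriptive statistic dropped or qualified in one table and one listing. No new samples are needed.
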